4 EXPERIMENTAL PLAN

4.1 Trial Design

This is a randomized, double-blind, placebo-controlled, parallel-group, outpatient trial. The trial will compare the efficacy and safety of 2 dose levels of GWP42003-P (150 mg twice daily [b.i.d.] and 500 mg b.i.d.) versus placebo in participants with schizophrenia who are experiencing an inadequate response to ongoing antipsychotic treatment.

The duration of the trial will be approximately 20 weeks, which includes a screening period (up to 4 weeks), a single-blind placebo run-in period (2 weeks), a double-blind treatment period (12 weeks), and a safety follow-up period (2 weeks).

After signing the informed consent form (ICF), participants will enter the screening period (Visit 1). The investigator will submit participants' eligibility forms for clinical surveillance and training (CST) review. The CST will evaluate the eligibility of participants and provide the outcome of the evaluation to the site. Participants cannot be enrolled until site personnel have received the final CST notification. Additional details for CST will be described in the study manual. At Visit 2 screened participants who continue to meet eligibility criteria will be randomized 1:1 to receive 150 mg b.i.d. or 500 mg b.i.d. dose matched volumes of placebo in a single-blind manner for the placebo run-in period. At Visit 3 (Day 1), participants who continue to meet the required eligibility criteria will be randomized 2:1 to receive GWP42003-P or placebo of equivalent volume to their placebo run-in allocation (Table 7.1-1) in a double-blind manner for the treatment period.

Randomization will be stratified by region (North America, Europe) and by sex (male, female).

A safety follow-up visit will be conducted 2 weeks after the last dose of IMP. If a participant discontinues IMP prematurely (i.e., before the end of the treatment period) they are required to attend an end of treatment (EOT) visit (±3 days) and complete the safety follow-up visit 2 weeks after their last dose. Participants are encouraged to attend any outstanding visits per the trial schema. If a participant prematurely discontinues IMP and withdraws from the trial without continuing trial visits as per the trial schema, they are required to attend an early termination (ET) visit upon withdrawal and complete the safety follow-up visit 2 weeks after their last dose.

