12.6 Reporting Procedures for All Adverse Events

All AEs (including SAEs) occurring during the trial will be reported on the running logs in the AE section of the eCRF. This includes all events from the time following screening (Visit 1) up to and including the post-trial follow-up visit (Visit 8), whether attributed to IMP or not and observed by the investigator or participant.

The following information will need to be provided for all AEs:

A) Adverse Event (Diagnosis or Syndrome if Known, or Signs and Symptoms)

Where the investigator cannot determine a diagnosis, signs or symptoms should be recorded in the AE section of the eCRF. Once a diagnosis has been determined the AE section of eCRF must be updated to reflect the diagnosis in replacement of the original symptoms. In circumstances where only a provisional diagnosis is possible (working diagnosis), the eCRF must be updated to reflect the provisional diagnosis in replacement of the original symptoms. In some circumstances it may be relevant for the investigator to include the symptoms alongside the diagnosis in the verbatim event description. However, the diagnosis (full or provisional) should be clearly stated, e.g., fever and malaise due to respiratory tract infection.

B) Adverse Event Start Date and Stop Date

The start and stop dates of the event must be provided. All AEs require these fields to be completed in full. Partial dates or missing dates are not normally acceptable and significant effort must be undertaken to obtain any unknown information. If a precise date is not known an estimated date should be provided instead. When a complete date cannot be given, record as much information as possible (i.e., month and year or,

Confidential Page 72 of 104 Clinical Protocol Template (Phase 2–4)

EudraCT Number: 2019-003369-16 Clinical Protocol Global V3, 23Mar2021

in exceptional circumstances, just year). When the actual start date becomes known the eCRF must be updated to replace the previously recorded date.

C) Outcome

The outcome of the event must be recorded accurately and classified as either:

- Fatal.
- Not recovered/Not resolved.
- Recovered/Resolved.
- Recovered/Resolved with sequelae.
- Recovering/Resolving.
- Unknown.

D) Severity

When describing the severity of an AE the terms mild, moderate, or severe should be used (see below). Clinical judgment should be used when determining which severity applies to any AE.

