If the severity of an AE fluctuates day-to-day, for example., a headache or constipation, the change in severity should not be recorded each time. Instead, only the worst observed severity should be recorded with AE start and stop dates relating to the overall event duration, regardless of severity.

A severe AE is not the same as an SAE. For example, a participant may have severe vomiting, but the event does not result in any of the SAE criteria above. Therefore, it should not be classed as serious. The severity of an AE will be recorded as 1 of the following:

- Mild: easily tolerated, does not interfere with normal daily activities, does not require intervention.
- Moderate: causes some interference with daily activities; minimal, local or non-invasive intervention indicated.
- Severe: daily activities limited or completely halted; intervention indicated.

E) Causality

Refer to Section 12.5 above.

EudraCT Number: 2019-003369-16 Clinical Protocol Global V3, 23Mar2021

F) Action Taken with Investigational Medicinal Product

This question refers to the action taken with the IMP due to an AE. The action with the IMP must be classed as:

- Dose increased.
- Dose not changed.
- Dose rate reduced.
- Dose reduced.
- Drug interrupted.
- Drug withdrawn.
- Not applicable.
- Unknown.

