13.6.4.2 Adverse Events

Adverse events will be coded according to the Medical Dictionary for Regulatory Activities dictionary.

A treatment-emergent adverse event (TEAE) is one that started, or worsened in severity or seriousness, following the first dose of IMP.

Descriptive presentations of TEAEs will be given by preferred term and SOC for the safety analysis set. The number of participants reporting at least 1 TEAE will be provided. AEs will be summarized in terms of the number of participants with at least 1 event (N) and the percentage of participants with at least 1 event (%).

The following summaries will be produced as a minimum:

- All-causality TEAEs.
- Treatment-related AEs.
- All-causality TEAEs by maximal severity.
- All-causality serious TEAEs.
- Treatment-related serious TEAEs.
- TEAEs reported as leading to permanent cessation of IMP.
- Fatal TEAEs.

Confidential Page 85 of 104

EudraCT Number: 2019-003369-16 Clinical Protocol Global V3, 23Mar2021

In the presentation of safety data, data from the GWP42003-P dose groups will be presented separately and compared with placebo. This will allow the possibility to explore any effects of the dose of IMP on safety endpoints.

Supportive summaries of ADRs will be presented.

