5.7.2 Adverse Events

All reported AEs will be classified by system organ class (SOC), preferred term and lower level term using Version 24.1 of MedDRA.

Summaries will be presented by treatment group as well as SOC and preferred term.

A treatment period treatment emergent AE (TEAE) is defined as an AE with a start date on or after the first dose of IMP during the treatment period (Day 1), or an AE that was present prior to the first dose of IMP during the treatment period but has increased its intensity during the treatment period.

If an AE has a partial start date and it is unclear from the partial date (or the stop date) whether the AE started prior to or post first dose of IMP then the AE will be considered treatment emergent and if it is unclear which period the event started, it will be assigned to both periods.

An AE will be considered treatment-related if the plausibility relationship to IMP is recorded on the CRF as 'yes'. If the data on plausibility relationship to IMP is missing then the AE will be considered treatment-related.

An AE will be considered leading to permanent discontinuation of IMP if the action taken with IMP is recorded on the CRF as 'trial medication stopped' or the outcome is recorded on the CRF as 'patient died'.

An AE will be considered leading to IMP dose reduction excluding permanent discontinuation if the action taken with IMP is recorded on the CRF as 'dose reduced', 'dose reduced temporarily' or 'trial medication interrupted'.

An AE will be considered leading to temporary IMP dose reduction if the action taken with IMP is recorded on the CRF as 'dose reduced temporarily'.

An AE will be considered leading to permanent IMP dose reduction excluding permanent discontinuation if the action taken with IMP is recorded on the CRF as 'dose reduced'.

An AE will be considered fatal if the outcome is recorded on the CRF as 'patient died'.

For the summary of TEAEs by maximal severity, for each participant, the worst severity recorded by preferred term, SOC and overall will be used for summary purposes. If severity is missing, the worst case (severe) will be assumed.

For summaries by resolution, AEs with an outcome of 'recovered' or 'recovered with sequelae' will be summarized as 'Resolved' and AEs with an outcome of 'continuing', 'patient died' or those with a missing outcome will be summarized as 'Not resolved'.

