For the summary of TEAEs by time of first onset of AE, data will be summarized for the treatment period separately under the following categories:

- Weeks 1–2 (Day 1 to 14).
- Weeks 3–4 (Day 15 to 28).
- Weeks 5–8 (Day 29 to 56).
- Weeks 9–12 (Day 57 to 84).
- >12 weeks (> Day 84).

The time to first onset of AE in treatment period will be calculated for TEAEs as:

$$\text{Start date of AE} - \text{Date of first dose of IMP in treatment period} + 1$$

If participants have multiple occurrences of an AE then the AE will be counted once for the first occurrence only. Percentages will be based on the number of participants in the safety analysis set who have a visit or follow-up call within each time period above.

For the summary of TEAEs by time to AE resolution, data will be summarized under the following categories:

- 1 week (≤ 7 days).
- 2 weeks (8–14 days).
- 3 weeks (15–21 days).
- 4 weeks (22–28 days).
- >4 weeks (>28 days).
- Ongoing (for AEs not resolved).

The time to AE resolution will be calculated for TEAEs as:

$$\text{Stop date of AE} - \text{Start date of AE} + 1$$

If participants have multiple occurrences of an AE then the AE will be counted once for the occurrence with the longest time to AE resolution. However, if any of the AEs are not resolved then the AE will be counted once within the 'Ongoing' category.

The start and stop day of the AE relative to the first dose of IMP will be calculated as per Section 5.1.2. For partial dates, if it is clear from the partial date that the start/stop day was prior to the first dose of IMP, then 'pre' will be listed, similarly if it is clear that the event was post the first dose of IMP then 'post' will be listed as the start/stop day as appropriate.

Listings will include the start and stop day of the AE, a flag for treatment emergence, and limited demographic information about the participant (age, sex, race and weight at screening).

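### SAP 5.7.2 counts any fatal AE as leading to permanent discontinuation of IMP, so a death after IMP had been completed or stopped for another reason would be misclassified

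*SAP*

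**What the plan says.** SAP 5.7.2 (Adverse Events) joins two conditions with 'or'. An AE leads to permanent discontinuation of IMP if the CRF shows "trial medication stopped' or the outcome is recorded on the CRF as 'patient died". The same section defines a fatal AE separately, by the outcome alone. It then defines a further category: "An AE will be considered leading to IMP dose reduction excluding permanent discontinuation if the action taken with IMP is recorded on the CRF as" reduced, temporarily reduced or interrupted. That definition looks only at the action field.

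The tables draw on TEAEs. SAP 5.7.2 defines a TEAE first as "an AE with a start date on or after the first dose of IMP during the treatment period (Day 1"), with a second limb for events that worsen during the treatment period. The onset table has an open last category, ">12 weeks (> Day 84").

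Protocol 13.6.4.2 lists, among the summaries required as a minimum, "TEAEs reported as leading to permanent cessation of IMP". Protocol 12.6, item F, says of the underlying field: "This question refers to the action taken with the IMP due to an AE", and its options include 'Not applicable'.

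On timing, Protocol 12.6 collects AEs "up to and including the post-trial follow-up visit (Visit 8"). Protocol 4.1 states: "A safety follow-up visit will be conducted 2 weeks after the last dose of IMP". It also encourages participants who stop IMP early to attend their remaining visits.

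**The concern.** A table of AEs leading to permanent discontinuation should hold events that caused someone to stop drug. An event that begins after the last dose cannot have done so. The fatal-outcome limb overrides the investigator's entry in the action field, even where that entry says no action was possible because IMP had already ended.

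Three things are at stake:

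- Table 14.3.5.1, and Table 14.3.5.2 for events judged related, could attribute a stop to the wrong event.
- They could then disagree with the withdrawal reasons in the disposition summary (SAP 5.4.1).
- The permanent-discontinuation and dose-reduction categories, whose labels make them mutually exclusive, would not be so for a fatal AE.

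**Working it through.** The documents give no figure for this rule, so there is none to reproduce. The check is whether the rule reaches deaths off drug, and what one such death would do.

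**Step 1: can an off-drug death be a TEAE?** Yes.

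- The first limb of the TEAE definition limits only the start of the window. The words about the treatment period there identify which first dose is meant.
- The onset table has a category beyond Day 84. Its percentages are based on participants with a visit or follow-up call in each period, and the only scheduled call is Visit 8 at Day 99 (Protocol Appendix 1). Events after dosing are evidently expected.
- Someone who stops IMP early and keeps attending can have an off-drug event well before Day 85.

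**Step 2: apply the rule to illustrative records.** The days are invented for the illustration. 'Proposed' refers to the definition under the fix.

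| Record | SAP 5.7.2 as written | Proposed |
|---|---|---|
| IMP completed Day 85; fatal AE starts Day 92; action 'Not applicable' | Flagged | Not flagged |
| IMP stopped Day 20 by participant's choice, not for an AE; fatal AE starts Day 30; no IMP action possible | Flagged | Not flagged |
| AE starts Day 80, no IMP action; IMP completed as planned Day 85; death Day 95 | Flagged | Not flagged |
| AE causes IMP to be stopped and so recorded; later death | Flagged | Flagged |
| Fatal AE while on IMP; action 'dose reduced' | Flagged, and also a dose reduction | Flagged only |

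The first three rows are the misclassification. The third shows that comparing AE onset with the last dose is not enough: onset precedes the last dose, yet IMP was completed as planned. The reference date has to be the date of death. The last row is the overlap: read literally, that event goes into Table 14.3.5.1 and also into Tables 14.3.5.3 and 14.3.5.7.

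**Step 3: size per affected participant.** Inputs: 80 randomized and allocation 2:2:1:1 (SAP 3.2). Assumptions: the ratio held, and everyone randomized was dosed.

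- Active arm: 80 × 2/6 = 26.7, about 27. One participant: 1/27 = 3.7 percentage points; two: 2/27 = 7.4. With 26 in the arm, 1/26 = 3.8.
- Pooled placebo: the same expected size, so also 3.7 points.
- One placebo volume group, shown separately in safety tables (SAP Table 1): 80 × 1/6 = 13.3, about 13; 1/13 = 7.7 points.
- All randomized: 1/80 = 1.25 points.

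The increment applies at participant level only if that person is not already correctly in the table for another AE. Otherwise only the system organ class or preferred term rows change.

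**The case against.** **The case is hypothetical.** The documents report no death, and the trial stopped at 80 randomized. This stands: the effect may be zero. A reader might infer that the discontinuation tables are in fact inflated, or try to estimate the share of deaths falling off drug. The documents give neither a death count nor a hazard, so they support neither reading.

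**Counting deaths is a sensible, conservative convention, and Protocol 13.6.4.2 gives no algorithm.** This largely stands. A death on drug does end treatment, and the protocol lists minimum summaries without defining them. The SAP rule is therefore at odds with the sense of that line rather than in flat contradiction with it. The defect is only the missing condition on IMP status.

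**SAP 5.1.3.4 ends the treatment period at Day 85, so a later event might be thought excluded.** The first limb of the TEAE definition does not tie onset to that period, and the follow-up call enters the onset denominators. Even if the limit applied, it would not help for someone who stopped IMP early and died before Day 85.

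**Other outputs would reveal the problem.** Fatal TEAEs have their own table (14.3.3.1), and AE listings carry start and stop days. This stands and lowers the importance. A reader might also take Table 14.3.5.1 as the trial's tolerability measure; the endpoint lists do not give it that role.

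**Missing causality is treated as 'Yes', so such a death might seem to pass easily into Table 14.3.5.2.** Protocol 12.5 requires a causality assessment for every AE, so little weight belongs there.

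**The CRF is not available.** The SAP's category strings ('trial medication stopped', 'patient died') differ from the protocol's ('Drug withdrawn', 'Fatal'), so the options open to a site for an off-drug death cannot be confirmed. This stands. Parts of the SAP near 5.7 are also redacted, but 5.7.2 is visible and points to no limit elsewhere.

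**A programmer might apply the exclusion in the dose-reduction label anyway.** Possibly, but the definition as written tests only the action field.

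**Conclusion.** The point holds in a narrow, conditional form and is minor. The rule as written would misclassify a fatal TEAE whenever IMP had been completed as planned, or permanently stopped for another reason, before the death. Separately, it lets one fatal AE meet two definitions that are labelled as exclusive; this is secondary.

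The size is about 3.7 percentage points in an active arm for each affected participant, assuming about 27 in the arm and no other qualifying AE in that person. With no such death it is zero. No efficacy result is touched, and no death is lost or hidden. It is still worth correcting, because this is a stated rule that gives a wrong classification rather than a detail left open.

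**What to change.** In SAP 5.7.2:

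1. Define an AE leading to permanent discontinuation by the recorded action taken with IMP.
2. Add a fatal AE without that action only if, before the date of death, IMP had been neither completed as planned nor permanently stopped for another reason.
3. Exclude any AE meeting this definition from the dose-reduction categories that are meant to leave out permanent discontinuation.
4. Check the action and outcome strings against the CRF version the SAP cites.

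All deaths stay in Table 14.3.3.1. This is a reporting definition only and alters no rule for managing participants.

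The cost is two or three sentences and a small program change. The program needs the date of death, the date IMP ended, and whether and why it ended, so it is slightly more than one date comparison. These items should already be in the AE, exposure and disposition records, and no new data collection is expected. If the SAP can no longer be amended before unblinding, apply the change as a described deviation in the clinical study report, as Protocol 13 provides.

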PP Per protocol

PRN Packaging reference number

PVD Pharmacovigilance Department

QTcF QT interval with Fridericia correction

RNA Ribonucleic acid

RTSM Randomization and Trial Supply Management

SAE Serious adverse event
SAP Statistical analysis plan

SCI-PANSS Structured Clinical Interview Positive and Negative Symptoms

Scale

SOC System organ class

SUSAR Suspected unexpected serious adverse reaction

SQLS Schizophrenia Quality of Life Scale

TBL Total bilirubin

TD Tardive dyskinesia

TEAE Treatment-emergent adverse event

THC Δ^9 -tetrahydrocannabinol

TRH Thyrotropin-releasing hormone

ULN Upper limit of normal

US United States

WOCBP Women of childbearing potential

Confidential Page 26 of 104

EudraCT Number: 2019-003369-16 Clinical Protocol Global V3, 23Mar2021

Definition of Terms

Term	Definition
Day 1	The day a participant first receives investigational medicinal product during the treatment period in this trial.
End of trial	Last participant last visit or last contact, whichever occurs last.
Enrolled participant	Any participant who has provided written informed consent to take part in the trial.
International normalized ratio	A calculation made to standardize prothrombin time.
Investigational medicinal product	Term used to describe both investigational active product and reference therapy (placebo).
Investigator	Trial principal investigator or a formally delegated trial physician.
QT interval	A measure of the time between the start of the Q wave and the end of the T wave in the heart's electrical cycle.

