12.8 Potential Cases of Drug-induced Liver Injury

All investigational sites are required to submit to the GW PVD the laboratory results for any participant after randomization that meets the criteria for the selected laboratory parameters as follows:

Confidential Page 74 of 104

EudraCT Number: 2019-003369-16 Clinical Protocol Global V3, 23Mar2021

- Serum ALT or AST > 3 × ULN with the appearance of fatigue, nausea, vomiting, right upper quadrant pain or tenderness, fever, rash, and/or eosinophilia (> 5%).
- ALT or AST $> 8 \times ULN$.
- ALT or AST $> 5 \times$ ULN for more than 2 weeks.
- ALT or AST \geq 3 × ULN and (TBL \geq 2 × ULN or INR \geq 1.5).

These reports must be sent to the GW PVD via email (see Appendix 2) within 24 hours of becoming aware of the results. In addition, please send a copy of the participant's baseline laboratory results with all reports to the GW PVD.

Abnormal values in AST and/or ALT concurrent with abnormal elevations in TBL that meet the criteria outlined above are considered potential cases of drug-induced liver injury and will be considered as protocol-defined criteria for treatment discontinuation and important medical events. The investigator will arrange for the participant to return to the investigational site as soon as possible (within 24 to 48 hours of notice of abnormal results) for repeat assessment of ALT, AST, TBL, alkaline phosphatase, and GGT, detailed history and physical examination. Participants should be followed in this way until all abnormalities have normalized (in the investigator's opinion) or returned to the baseline state. However, if the above transaminase elevation criteria are confirmed by the first set of follow-up laboratory tests, the participant must be withdrawn from the trial.

Elevations in ALT or AST $> 3 \times \text{ULN}$ or TBL $> 2 \times \text{ULN}$ alone are not considered potential cases of drug-induced liver injury, but will be followed as detailed above, within 72 hours' notice of abnormal results. If the participant cannot return to the investigational site, repeat assessments may be done at a local laboratory and the results sent to GW PVD.

12.9 Notification of Safety Information to Investigators, Regulatory Authorities and Institutional Review Board or Independent Ethics Committee

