APPENDIX 1 SCHEDULE OF ASSESSMENTS

Period	Screening Period	Placebo Run-in Period 2		Safety Follow-up Period				
Visit Number			3	4	5	6	7 EOT/ET ^a	8 Telephone call
Week	-6	-2		2	4	8	12	14
Day	−42 to −15	-14	1 (Baseline)	15	29	57	85	99
Visit Window (Days)			+3	±3	±3	±3	±3	±3
Informed consent	X							
Eligibility criteria	X^p		X					
Placebo-response training video ^b		X	X				X	
Demographics	X							
Cannabis use survey ^c	X	X	X	X	X	X	X	
Medical history	X							
Psychiatric history	X							
Physical examination ^d	X		X				X	
Body weight, BMI, waist circumference and height ^e	X		X	X	X	X	X	
Vital signs ^{f, g}	X	X	X	X	X	X	X	
ECG ^{f, h}	X		X				X	
Chemistry	X		X		X		X	
Hematology	X		X		X		X	
Serology ⁱ	X							
PK blood sampling ^j	X			X			X ^q	
Biomarker sampling			X				X	

Study Code: GWAP19030 EudraCT Number: 2019-003369-16 Clinical Protocol Global V3, 23Mar2021

Period	Screening Period	Placebo Run-in Period		Safety Follow-up Period				
Visit Number			3	4	5	6	7 EOT/ET ^a	8 Telephone call
Week	-6	-2		2	4	8	12	14
Day	-42 to -15	-14	1 (Baseline)	15	29	57	85	99
Visit Window (Days)			+3	±3	±3	±3	±3	±3
Pharmacogenomic DNA sampling			X					
Pharmacogenomic RNA sampling			X				X	
Urinalysis	X		X	X		X	X	
Drug screen ^k	X		X				X	
Pregnancy test (for WOCBP)	X		X		X	X	X	
ESRS ¹	X		X	X	X	X	X	
C-SSRS	X	X	X	X	X	X	X	
MINI for Psychotic Disorders Studies	X							
PANSS ^m	X	X	X	X	X	X	X	
CGI-S	X	X	X	X	X	X	X	
CGI-I				X	X	X	X	
PGIC			X	X	X	X	X	
CDSS		X	X				X	
BACS	X		X				X	
SQLS		X	X				X	
BAS-MPsQ		X			1	X		
EXP-MPsQ			X		1			
PER-MPsQ		X						

EudraCT Number: 2019-003369-16 Clinical Protocol Global V3, 23Mar2021

Period	Screening Period	Placebo Run-in Period		Т	Safety Follow-up Period			
Visit Number	1	2	3	4	5	6	7 EOT/ET ^a	8 Telephone call
Week	-6	-2		2	4	8	12	14
Day	-42 to -15	-14	1 (Baseline)	15	29	57	85	99
Visit Window (Days)			+3	±3	±3	±3	±3	±3
Randomization		X	X					
Dispense IMP ^{n, o}		X	X	X	X	X		
Return IMP			X ^r	X	X	X	X	
IMP Adherence System and Compliance Check ^S		X	X	X	X	X	X	
AEs		X	X	X	X	X	X	X
Previous and concomitant medication	X	X	X	X	X	X	X	X

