- h. An ECG will be performed after 5 minutes in a supine position, if possible. The ECGs should be done in triplicate at screening and baseline to ensure that QTcF < 450 msec (males)/ < 470 msec (females). Any subsequent ECG should be done once and should be repeated 2 times in cases where withdrawal criteria are met (QTcF ≥ 500 msec).
- i. To include HIV, hepatitis B, and hepatitis C.
- j. Plasma concentrations of the background antipsychotic medications will be assessed at Visit 1 and predose relative to the administration of IMP at Visit 4 and Visit 7.
 - CBD and its major circulating metabolites will be assessed at Visit 1 and relative to the administration of IMP at Visits 4 and 7. A PK sample will be collected before the participant's morning dose of IMP and within 12 hours (-3/+6 hours) since last IMP dose (Visit 4 and Visit 7). Following collection, the IMP will be administered with a meal of at least 300 kcal to be provided. At Visit 1, only a baseline PK sample will be collected. At Visit 4 and Visit 7, samples to determine concentrations of CBD and its major circulating metabolites will be collected pre- and postdose, relative to IMP, at a timepoint between 2 to 3 hours. Thereafter optional PK sampling may be collected at postdose time points between 4 to 6 hours and 8 to 10 hours.
- k. A drug screen test (urine) will include alcohol, amphetamines (including ecstasy), barbiturates, benzodiazepines, cocaine, methadone, opiates, and THC. THC will be blinded from Visit 3 to the end of the trial.
- 1. Assessment to be conducted prior to dosing of any regular medication prescribed for the management of extrapyramidal side effects (e.g., anticholinergics, beta-blockers etc.).
- m. Every effort should be made to include informant information in the PANSS assessment through administration of the Informant Questionnaire PANSS. If contact with a participant's informant cannot be made within 3-day window from the date of the study visit, either by phone or in person, then the informant interview should not be considered a barrier to visit progression.
- n. IMP is to be taken orally b.i.d., (e.g., morning and evening) preferably within 30 minutes of a meal using the syringe(s) provided. Participants will be asked to return all IMP (used and unused) at each relevant visit. The first dose of IMP at Visit 2 should be taken at the site.

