5. STATISTICAL METHODS

5.1 General Considerations

In all tables, listings and figures, the treatment arms will be referred to and labelled as per [Table 1](#).

Table 1 Study Treatments

Endpoint	Actual Treatment	Treatment Label
Efficacy and Exploratory	Pooled Placebo	Placebo
Safety	150 mg b.i.d Placebo	Placebo 300 mg
	500 mg b.i.d Placebo	Placebo 1000 mg
	Pooled Placebo	Pooled Placebo
All	150 mg b.i.d GWP42003-P	300 mg
All	500 mg b.i.d GWP42003-P	1000 mg

For safety tables where placebo is split by dose, an additional Pooled Placebo column will be included.

In all tables, listings and figures, the study visits will be referred to and labelled as per [Table 2](#).

Table 2 Study Visits

Actual Visit	Visit Label
Visit 1: Screening	Screening
Visit 2: Placebo Run-in	Day -14
Visit 3: Day 1, baseline visit	Day 1
Visit 4: Day 15	Day 15
Visit 5: Day 29	Day 29
Visit 6: Day 57	Day 57
Visit 7 / Early Termination / End of Treatment*: Day 85	Day 85
Visit 8 Telephone call: Day 99	Safety Follow-Up

*If a participant discontinues IMP prematurely (i.e., after Visit 3 but before Visit 7) they are required to attend an End of Treatment visit and complete the safety follow-up visit 2 weeks after their last dose. The End of Treatment visit will be assigned to the nearest post-baseline visit (for which the assessment is scheduled to be performed), based on the trial day of the visit.

Unless stated otherwise, continuous variables will be summarized showing the number of non-missing values (n), mean, standard deviation, median, minimum and maximum and categorical variables will be summarized showing the number and percentage of participants falling into each category.

Minimum and maximum values will be presented to the same decimal precision as the raw data. Mean and median will be presented to 1 more decimal place than the raw data, and standard deviation to 2 more decimal places than the raw data. Percentages will be presented to 1 decimal place.

All analyses and summaries will be produced using SAS Version 9.4 or higher.

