5.1.2 Day Numbering

The first day of treatment in the treatment period (Day 1) will be taken from 'Date of first dose of IMP in Treatment Period' on the Randomization CRF.

Any days prior to Day 1 will be numbered relative to this day and calculated as:

Date – (Date of Day 1)

to give Day -1, -2, -3 etc.

Any days post Day 1 will be calculated as:

Date - (Date of Day 1) + 1

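### SAP 5.7.2 time-of-onset table: placed by actual study day, a full attender with an early Visit 4, 5 or 6 and a non-early next visit leaves a period's denominator while still under AE observation

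*SAP*

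**What the plan says.** SAP 5.7.2 plans a summary of treatment-emergent AEs by time of first onset (Table 14.3.2.6). It has five periods defined by day: 1–14, 15–28, 29–56, 57–84 and after Day 84. Onset is the AE start date minus the date of first treatment-period dose, plus 1. The base for each percentage is the "number of participants in the safety analysis set who have a visit or follow-up call within each time period above".

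Study days run from an actual date. In SAP 5.1.2, "The first day of treatment in the treatment period (Day 1) will be taken from" the first-dose date on the Randomization CRF, and the protocol's Definition of Terms makes Day 1 "The day a participant first receives investigational medicinal product during the treatment period in this trial".

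Protocol Appendix 1 puts Visits 4, 5, 6 and 7 on Days 15, 29, 57 and 85 and the Visit 8 telephone call on Day 99, each with a window of 3 days either way. SAP 5.1 adds that in its outputs "the study visits will be referred to and labelled as per" Table 2, which names visits by nominal day.

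Protocol 12.6 has all AEs recorded from screening up to and including Visit 8.

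**The concern.** Each middle period holds one scheduled visit, and its nominal day is the first day of the period. Coming one day early, which the window allows, moves that visit into the previous period. Unless the following visit is early too, the period is left with no scheduled contact. The participant then drops out of that period's denominator without having missed anything and without any break in AE recording. The SAP does not limit the numerator to participants in the denominator, so an AE starting on Day 20 could be counted for someone outside the base.

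The Weeks 3–4, 5–8 and 9–12 columns would then depend on the punctuality of visits rather than on who was being observed. The table exists to show when AEs start, and its columns would not be on a common footing.

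**Working it through.** The plan gives no figure to reproduce here. The check places visits in periods and counts the empty ones.

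**Inputs.** Periods: SAP 5.7.2. Nominal days: SAP Table 2 and Protocol Appendix 1. Window of ±3 days: Protocol Appendix 1. Visit 3 is taken as Day 1, as both documents schedule it.

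| Contact | Nominal day | Window | If early | If not early |
|---|---|---|---|---|
| Visit 4 | 15 | 12–18 | Weeks 1–2 | Weeks 3–4 |
| Visit 5 | 29 | 26–32 | Weeks 3–4 | Weeks 5–8 |
| Visit 6 | 57 | 54–60 | Weeks 5–8 | Weeks 9–12 |
| Visit 7 | 85 | 82–88 | Weeks 9–12 | >12 weeks |
| Visit 8 (call) | 99 | 96–102 | >12 weeks | >12 weeks |

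**Rule.** For a full attender, a middle period is empty exactly when its opening visit is early and the next visit is not. Two examples:

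- Days 1, 14, 29, 57, 85, 99: no contact in Days 15–28, so the participant is dropped from Weeks 3–4 only.
- Every visit 3 days early (Days 12, 26, 54, 82, 96): dropped from no period.

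Listing all 7^5 = 16,807 in-window combinations for Visits 4 to 8 confirms the rule without exception. Each middle period is empty in 4,116 of them, which is 3/7 × 4/7 = 12/49 = 24.5%. Weeks 1–2 and >12 weeks are never empty.

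**Size under an assumption.** Let each visit be early with chance p, independently. The share of full attenders dropped from a given middle period is p(1−p):

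- p = 0: 0
- p = 5%: 0.05 × 0.95 = 4.8%
- p = 10%: 0.10 × 0.90 = 9%
- p = 50%, the maximum: 0.50 × 0.50 = 25%

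The 24.5% above is the case of visit days uniform over the window (p = 3/7). If early attendance is correlated within a participant (latent normal correlation 0.5), the share is p minus the chance that both visits are early: 3.8% at p = 5% and 6.8% at p = 10%.

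**What this does to a percentage.** SAP 3.2 reports 80 randomized. At the planned 2:2:1:1 ratio that is 80 × 2/6 = 26.7 per active arm and 80 × 1/6 = 13.3 per placebo dose column. Suppose everyone is a full attender and two first onsets stay in the numerator:

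| Share dropped | Arm of 27 | Column of 13 |
|---|---|---|
| 0 | 2/27 = 7.4% | 2/13 = 15.4% |
| 4.75% | 2/(27 × 0.9525) = 7.8% | 2/(13 × 0.9525) = 16.2% |
| 9% | 2/(27 × 0.91) = 8.1% | 2/(13 × 0.91) = 16.9% |
| 24.5% | 2/(27 × 0.755) = 9.8% | 2/(13 × 0.755) = 20.4% |

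The denominators are expected values, not possible counts. At p = 5% and 10% the expected loss from an arm of 27 is 27 × 0.0475 = 1.3 and 27 × 0.09 = 2.4 participants.

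If the numerator were instead limited to the same base, percentages would not be inflated on average, but a share p(1−p) of full attenders' first onsets in that period would vanish from the table.

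**The case against.** The best reply is that visits are meant to be placed by label. The periods after the first open on Days 15, 29, 57 and 85, exactly the nominal days of Visits 4 to 7, and Table 2 labels apply to all outputs. On that reading no full attender is dropped. This stands as a possible intention, but the SAP does not state it for this table. Table 2 governs naming, and where the SAP wants a contact moved to a scheduled visit it says so, as for End of Treatment data (Table 2 footnote and 5.5.2.1). The onset periods and the onset formula are both in actual study days.

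Three further points stand:

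- The magnitude rests on assumed visit timing. Nothing in the documents supports the 24.5% case in particular.
- An unscheduled visit can fill the gap. Protocol 12.8 provides for some after abnormal liver tests: "The investigator will arrange for the participant to return to the investigational site as soon as possible".
- The table is descriptive and is not among the minimum AE summaries in Protocol 13.6.4.2. AE start days are listed anyway, and one extra event moves an arm of 27 by 1/27 = 3.7 points, more than the denominator effect at p = 5% or 10%.

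A reader might also infer that Weeks 1–2 loses participants, if the first treatment-period dose is taken the day after Visit 3. The documents equate Visit 3 with Day 1 and do not support that extension.

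**Conclusion.** The concern holds as a minor point. On actual study days, the more natural reading under SAP 5.1.2, the stated base drops fully compliant participants from Weeks 3–4, 5–8 or 9–12 while their AEs are still being recorded. The share is unknown; p(1−p) per middle period is a guide under independent early attendance, and the worked percentages also assume that every arm member is a full attender.

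Two stronger conclusions are tempting but unsupported. One is that the table systematically overstates AE rates. Dropping observed participants raises a percentage, but a participant last seen on a period's first day is counted in full, which lowers it, so the net direction is not certain. The other is that the comparison between arms is biased. All arms share one blinded visit schedule, so none is expected. Efficacy and overall TEAE incidence do not use this denominator.

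**What to change.** In SAP 5.7.2, state that visits and calls are placed by actual study day, and base each period's percentage on safety-set participants still under AE observation at its start: those whose last visit or follow-up call is on or after the first day of the period. Keep the five periods unchanged. A full attender then counts in all five, because the Visit 8 call falls on Days 96–102.

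AE dates should not determine the denominator, since that would make it depend on the outcome. Any first onset after a participant's last contact can be footnoted or listed separately.

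The cost is one or two SAP sentences and a small change to one table program. No new data are needed: visit dates are already in Listing 16.2.1.4. The remaining limitation is that this is not a person-time measure, so a participant last seen on a period's first day still counts in full.
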